#### **1.4.3 Sub-sample analysis**

We performed sub-sample analysis on the study participants who received the Full-Tech intervention (see Equation 2). Instances where this sub-sample analysis was not conducted is noted in the description of that outcome.

Eq. 2:

$$\text{If } X_{Tech} = \text{Full; } y = X_{Touch}$$

#### **1.4.4 Distributional assumptions**

Prior to analysis, we will conduct an examination of the data to assess model fit for each hypothesis (i.e., Poisson, Negative Binomial, etc.).i

---

i Preliminary analysis revealed wide variance in the length of time that patients had a tablet, which we termed ‘provision length’. This provision length was included as an exposure in the model fitting process. Analysis after data collection suggested that the ANOVA model was a poor choice for the distribution of the data. Poisson models were excluded because of the foundational assumption—namely that the mean and variance of the response variable are the same. In the data, the variance was significantly greater than the mean, leading this model to significantly underestimate true variability in the data. Subsequent outlier analysis suggested no improvement. The negative binomial model was specified four ways: (1) negative binomial; (2) negative binomial with the provision length adjustment; (3) zero truncated; (4) zero truncated with the provision length adjustment. The zero truncated model with length of provision as an exposure variable provided the best relative fit when comparing information criteria values. However, this improvement was viewed as marginal relative to the negative binomial model specification. For this reason and to account for the heterogeneity in provision length, all count outcomes were fit using a negative binomial model with the provision length adjustment.

#### **1.4.5 Defining MyChart Bedside use sessions**

A new MyChart Bedside use session was identified in the log files in two ways: (1) a “identify user with lock” action; or (2) any user action that occurred more than 15 minutes after the previous action. Some session periods contained no active tasks as defined in Section 6.3.5 in the Final Protocol. These inactive sessions were dropped from analyses. The “identify user with lock” action that marked the beginning of a session sometimes occurred multiple times sequentially without any other actions occurring. Retaining these recurring actions would create sessions with only a login action. To eliminate this problem, sequential “identify user with lock” actions were dropped.

#### **1.4.6 Defining MyChart use sessions**

MyChart log files contained timestamped records of patient actions on the outpatient portal. This data was processed to obtain information about the number of sessions associated with each unique study participant. For MyChart, a session was defined by a sequence of actions linked to a patient’s medical record number (MRN), with the first action typically being a ‘login’ and the last one a ‘logout’. In the case of MyChart sessions, at times patients did not actively logout of the application. Using the protocol described by Huerta, et al., we imposed a limit of 22 minutes as the length of time a patient was allowed to stay inactive before a ‘logout’ was imputed into the data. All actions occurring after the time limit were considered part of a new session.

Additionally, sessions of length zero were discarded from the dataset.

#### **1.4.7 Scaling analysis for Likert items**

For Likert scale survey items, each survey item was modeled using one of three approaches:

1. An ordinary least squares (OLS) linear regression model with each Likert scale response treated as a continuous variable;
2. A logistic regression model with the Likert scale dichotomized to two “positive” responses versus three “not positive” responses; and
3. A logistic regression model with the Likert scale dichotomized to one “most positive” response versus all other responses.

The OLS model was assumed to be the most parsimonious model, making it the default model choice. However, OLS model assumptions were tested to confirm that this choice was appropriate. Between the two logistic models, Model #3 was considered to be the more restrictive model choice and thus provided a more conservative estimate of the effect of the study on the outcome. Model choices are specified below in relation to each outcome.

#### 1.4.8 Cutoff date determination

Two options were considered for both the pre-study enrollment and post-discharge cutoff dates as specified in subsequent sections: 90 days (approximately three months) and 180 days (approximately six months) before/after the hospital encounter in which an individual was enrolled in the study. The actual cutoff date was determined after examining the cumulative distribution of MyChart adoption over the course of the year preceding/following hospital discharge to identify a meaningful endpoint.ii

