Our proposed four-year study used a mixed-methods approach to evaluate a pragmatic randomized controlled trial (RCT) studying the effectiveness of a High-Tech Intervention (MyChart Bedside, the inpatient portal), and an accompanying High-Touch Intervention (training patients to use the portal to manage their care and conditions) in a sample of hospitalized patients. This study measured how a patient portal tailored to the inpatient stay could improve patient experience and increase patient engagement by 1) improving patients' perceptions of the process of care while in the hospital, 2) increasing patients' self-efficacy for managing their health and health care, and 3) facilitating continued use of a patient portal for care management activities after discharge. In addition, we aimed to enhance patients' use of the patient portal available to outpatients, MyChart, once they were discharged.

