2.2 Objectives

The ***High Tech and High Touch (HT2): Transforming patient engagement throughout the continuum of care by engaging patients with portal technology at the bedside*** study at OSU Wexner Medical Center (OSUWMC) sought to study how the deployment of a commercial (i.e., Epic Systems) inpatient portal, MyChart Bedside, impacted identified patient outcomes. To evaluate the impact of function set and training

on inpatient (i.e., MyChart Bedside) and outpatient (i.e., MyChart) portal use, the HT2 Study²⁰ was designed as a large-scale, pragmatic randomized controlled trial across six hospitals in a healthcare system.

Using a two-by-two factorial design, HT2 simultaneously examined the effects of two approaches to portal training with two versions of the inpatient portal. HT2 was designed to test four study hypotheses:

Hypotheses related to primary outcomes:

H1: Patients assigned to the High intervention levels for Tech and Touch will demonstrate higher use of MyChart Bedside.

H2: Patients assigned to the High intervention levels for Tech and Touch will demonstrate higher levels of satisfaction with (H2a) and involvement in (H2b) their care experience.

Hypotheses related to secondary outcomes:

H3: Patients assigned to the High intervention levels for Tech and Touch will demonstrate higher rates of outpatient portal adoption (i.e., of Epic's MyChart) for those admitted without prior outpatient portal use (H3a), and higher use of MyChart for those admitted who had previously used the outpatient portal (H3b).

H4: Patients assigned to the High intervention levels for Tech and Touch will demonstrate higher levels of self-efficacy.

To prevent outcome reporting bias and data-driven analysis of results, we produced this detailed statistical analysis plan. The plan was originally developed and drafted prior to examination of the data, and in the absence of randomization knowledge. The plan has been revised as the analysis has proceeded.

Section 3: Study methods

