#### 1.5.1 Outcome 1 – Number of MyChart Bedside sessions within the enrollment admission was dependent on treatment

*Dependent variable specification:* The count of MyChart Bedside sessions for the admission associated with study enrollment.

- Enrollment admission was defined as the admission when the patient was enrolled in the study.

*Statistical model:* Negative binomial model with non-interacted and interacted study arms as binomial predictors.

---

ii Preliminary analysis of adoption rates for the outpatient portal revealed a rapid decrease in the numbers following the first few months, which motivated us to set the value for the cutoff date at 90 days in order to more conservatively attribute portal use to an individual's participation in the study.

*Covariates:* No covariates were added to this analysis.

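### The 90-day window for H3 was chosen after looking at outpatient portal adoption; it also cuts the session counts of existing users, and no 180-day sensitivity analysis is planned.

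*SAP*

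**What the plan says.** SAP 1.4.8 considers two windows, "90 days (approximately three months) and 180 days (approximately six months) before/after the hospital encounter" of enrollment. On the choice between them it says: "The actual cutoff date was determined after examining the cumulative distribution of MyChart adoption". The curve was examined "over the course of the year preceding/following hospital discharge to identify a meaningful endpoint".

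Footnote ii to that section gives the finding, "Preliminary analysis of adoption rates for the outpatient portal revealed a rapid decrease in the numbers following the first few months", and the decision. The finding "motivated us to set the value for the cutoff date at 90 days in order to more conservatively attribute portal use" to study participation.

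SAP 1.7 then uses this cutoff throughout H3. It separates New from Never users (Outcomes 1 to 3), and it ends the period over which sessions are counted for New users (Outcome 4) and Prior users (Outcome 5, which tests H3b). SAP 1.7 plans no analysis at 180 days or at any other window.

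On the status of the plan, Protocol 2.2 states: "To prevent outcome reporting bias and data-driven analysis of results, we produced this detailed statistical analysis plan". The same paragraph says that the first draft preceded examination of the data and knowledge of randomization, and that the plan was revised while the analysis went on. H3 is listed there as a secondary hypothesis.

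**The concern.** Two things look wrong.

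First, post-enrollment adoption is what H3a measures, and its observed distribution was used to decide the period over which it is measured. The plan states that it exists to guard against data-driven analysis. The assurance about randomization knowledge is attached to the first draft, and nothing extends it to the moment when the cutoff was picked.

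Second, the reason drawn from the curve does not carry over to every outcome that uses the cutoff. Prior users had adopted before enrollment. When other people first adopt says nothing about how long these users stay active.

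At stake is whether a reader can tell an H3 finding that holds in general from one that holds only at 90 days. With a single window planned, the reader cannot.

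**Working it through.** The plan states no sample size, power or error rate for H3, so there is no figure to reproduce. The planning figure in Protocol 3.4 (3,872 participants, changes of 2.2% to 3.8%) concerns HCAHPS satisfaction scores and has no bearing here. The check is therefore a comparison of sections, plus one small illustration.

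**Step 1. What was inspected, and what it defines.** The curve in SAP 1.4.8 shows MyChart adoption. SAP 1.7.1 to 1.7.3 analyze MyChart adoption. The quantity inspected is the H3a outcome.

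**Step 2. Was the inspection blind to arm?** SAP 1.4.8 and footnote ii speak of adoption in general and mention neither arms nor pooling. Protocol 3.6 says that outcomes and their association with the interventions were reviewed only on study completion. That does not settle whether arms were visible when the cutoff was set. The question stays open.

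**Step 3. What the cutoff does to each outcome.**

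| H3 outcome (SAP) | Effect of moving from 90 to 180 days |
|---|---|
| 1 (1.7.1) New v Never | Adopters between the two cutoffs move from 0 to 1 |
| 2 (1.7.2) Post-discharge New v Never | The same move |
| 3 (1.7.3) Admission New v Never | Cases are fixed during the stay; later adopters leave the comparison group |
| 4 (1.7.4) Sessions, New users | Both the counting period and the set of New users change |
| 5 (1.7.5) Sessions, Prior users | Only the counting period changes |

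The adoption curve has a direct bearing on Outcomes 1 and 2. It has none on Outcome 5, where every participant had adopted before enrollment.

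**Step 4. Is the shorter window conservative?** Let w be the share of control-arm sessions over 180 days that fall in the first 90. Let RR1 and RR2 be the rate ratios in the first and second 90 days. Then

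RR over 180 days = w × RR1 + (1 − w) × RR2.

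The documents give none of these inputs, so all values below are hypothetical.

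- Fading effect (RR1 = 1.20, RR2 = 1.00, w = 0.5): 0.5 × 1.20 + 0.5 × 1.00 = 1.10. The 90-day analysis shows 1.20.
- The same effect with use concentrated early (w = 0.8): 0.8 × 1.20 + 0.2 × 1.00 = 1.16, against 1.20.
- Growing effect (RR1 = 1.00, RR2 = 1.20, w = 0.5): 0.5 × 1.00 + 0.5 × 1.20 = 1.10. The 90-day analysis shows 1.00.

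The 90-day window gives the larger estimate when the effect fades and the smaller one when it grows. Whether it is conservative depends on a time pattern that only a second window would reveal.

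**Step 5. Are the data in hand?** The curve examined ran for a year, which covers 180 days. The MyChart logs for the longer window therefore appear to be available already.

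**The case against.** The case for leaving the plan alone has real substance. The choice was between two named options and is disclosed with a reason. SAP Section 2 describes the original plan as exploratory and flexible. A window set from a curve pooled over arms would be expected to cause little or no inflation of type I error. Footnote ii also gives a second reason, attribution to study participation. It is stated for portal use in general and so covers the H3b counts too. H3 is secondary.

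Most of this stands, and it rules out some stronger readings that a reader might infer.

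- **That the H3 error rate is inflated by a known amount.** This would need the window to have been picked on visible arm comparisons, which no section says. Even then, the rate for the better of two 5% tests would run from 5% (perfectly correlated) to 1 − 0.95² = 9.75% (independent). The documents give no correlation to place it in that range.
- **That 180 days was promised follow-up.** It was only a candidate. The aim in Protocol 2.1 of "facilitating continued use of a patient portal for care management activities after discharge" names no horizon, and six months is the survey schedule.
- **That the choice was concealed.** It is stated openly.

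Two things do not fall to the objection. Disclosing a data-informed window does not tell the reader whether the result depends on it. And the attribution reason is thin, because in a randomized comparison attribution comes from the arms and Step 4 shows that shortening the window has no fixed direction of effect.

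**Conclusion.** The point holds as a cheap improvement, not as a flaw that invalidates H3. The 90-day window was set after inspection of the H3a outcome, its adoption rationale does not fit the H3b session counts, and no second window is planned. Bias in the arm comparison is possible but not shown, and its size cannot be computed from the documents. The rate ratios in the working illustrate direction only and do not estimate what happened in this trial.

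The conclusion assumes that the logs behind the one-year curve cover 180 days for essentially all participants. If they do not, the 180-day analysis would need its own statement of who is included.

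**What to change.** 1. Keep 90 days as the main window, labelled as chosen after adoption data were viewed.
2. Add 180-day results as a planned sensitivity analysis for H3 Outcomes 1, 2, 4 and 5. Outcome 5 matters most, because only its counting period changes; hold its pre-enrollment covariate the same in both runs. For Outcome 4, note that the set of New users changes as well. Outcome 3 can be left out, since the cutoff alters only its comparison group.
3. State in SAP 1.4.8 whether the adoption curve was viewed pooled over arms and blind to assignment.
4. Justify the window for the session counts separately from the adoption curve.
5. Describe any H3 conclusion that differs between windows as dependent on the window. No further rule for declaring H3 supported is needed; one added now would itself be post hoc, and nested windows make agreement in direction a weak check.

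While editing, correct the pointer in SAP 1.7, which sends the reader to 1.4.7 for the cutoff when it is in 1.4.8. Also say whether the window runs from the encounter (1.4.8) or from enrollment (1.7.4 and 1.7.5).

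The cost is rerunning models already specified on existing logs. The downside is more estimates with no multiplicity adjustment, so they should be labelled as sensitivity results.

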#### 1.4.9 Facility Transfer Sensitivity Analysis

Baseline characteristics were summarized, including age (median), gender (male, female percentages), race (White, Black, Other percentages), length of stay (days), and the Charlson comorbidity index (median, treated as a continuous score). Baseline characteristics were compared using analysis of variance (ANOVA) or t-tests, as appropriate, to examine equivalence between the four study arms and the impact on the model estimates for patients who were transferred between facilities was negligible.

### 1.5 Hypothesis 1: Inpatient portal use

*H1: Individuals assigned to the High intervention levels for Tech and Touch will demonstrate higher use of MyChart Bedside.*

We operationalized higher use in this hypothesis in three ways:

1. Frequency of use
2. Comprehensive use

#### 1.5.1 Outcome 1 – Number of MyChart Bedside sessions within the enrollment admission was dependent on treatment

*Dependent variable specification:* The count of MyChart Bedside sessions for the admission associated with study enrollment.

- Enrollment admission was defined as the admission when the patient was enrolled in the study.

*Statistical model:* Negative binomial model with non-interacted and interacted study arms as binomial predictors.

---

ii Preliminary analysis of adoption rates for the outpatient portal revealed a rapid decrease in the numbers following the first few months, which motivated us to set the value for the cutoff date at 90 days in order to more conservatively attribute portal use to an individual's participation in the study.

*Covariates:* No covariates were added to this analysis.

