#### 1.4.2 Analytic framework

A review of factorial randomized control trials identified that the appropriate analytics model, in general, would adhere to Equation 1 (see below), assuming that the basic functional form for regression is the appropriate approach. This approach was used per Montgomery et al. Variations to this functional form are noted below.

$$\text{Eq. 1: } y = X_{Tech} + X_{Touch} + X_{Tech*Touch}$$

To address potential differences in variance associated with the multi-site and pragmatic aspects of the study (e.g., expansion of the study after it was originally conceptualized and operationalized, differences in policies and procedures across hospitals and units), we performed cluster-robust standard errors in the estimation of the outcomes. The analysis clusters study participants by the hospital where the study participant was enrolled. To validate this assumption, a sensitivity analysis was performed on patients transferred to different hospitals within the medical center.

Further, to account for heterogeneity in duration of patient access to the inpatient portal, we included the length of tablet provisioning, measured in days, as an offset parameter in all models.

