### 1.5.3 Outcome 3 – MyChart Bedside use (by function) was dependent on Touch arm.

*Sub-sample specification:* As a function of the hypothesis and outcome specification, this analysis was not subject to sub-sample analysis as described in section 1.4.2. This analysis only used the Full-Tech arms, and therefore only used the Touch predictor in the statistical model.

*Outcome specification:* Proportion of total use, calculated for each user by dividing the sum of actions in a given function from the total sum of user actions during their enrollment admission accounted for by each function.

*Statistical model:* For each function, a fractional logistic regression model was performed, with use proportion as the response variable and Touch status as the explanatory variable.

*Covariates:* No covariates were added to this analysis.

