### 1.6.1 Outcome 1 – Patient satisfaction was dependent on treatment

*Outcome specification:* Variations of this outcome were available in each survey. The following 5-point Likert scale survey items were explored as individual items dichotomized to one “most positive” response versus all other responses:

- **15-day Post-discharge survey:** In your most recent hospital experience, how satisfied were you with the interactions you had with your healthcare professionals?
- **15-day Post-discharge survey:** In your most recent hospital experience, how satisfied were you with how well your healthcare professionals responded to your concerns?
- **6-month Post-discharge survey:** In the past six months, how satisfied were you with the interactions you had with your healthcare professionals?
- **6-month Post-discharge survey:** In the past six months, how satisfied were you with how well your healthcare professionals responded to your concerns?

*Statistical Model:* Logistic regression models with and without an interaction of Tech and Touch were reported.

*Covariates:* The corresponding survey item from the Admission Survey was used as a covariate for the items listed above. The two relevant survey items were:

- **Admission survey:** In the past 12 months, how satisfied were you with the interactions you had with your healthcare professional?
- **Admission survey:** In the past 12 months, how satisfied were you with how well your healthcare professionals responded to your concerns?

*Sub-sample analysis:* No sub-sample analyses were considered for this outcome.

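### SAP 1.4.2 makes a model with the Tech-by-Touch product the general form, but neither document states the coding or which model or coefficient tests H1 to H4

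*SAP*

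**What the plan says.** SAP 1.4.2 states that "the appropriate analytics model, in general, would adhere to Equation 1", whose three terms are Tech, Touch and their product. Outcome sections may vary this.

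- **H1 outcomes 1 and 2, and H3 (SAP 1.5.1, 1.5.2, 1.7.1 to 1.7.5).** For H1 outcome 1 the model is a "Negative binomial model with non-interacted and interacted study arms as binomial predictors"; the others are worded alike. H3 outcomes 4 and 5 point to Equations 3 and 4, each a single equation containing the product.
- **H2 (SAP 1.6.1 to 1.6.2b).** "Logistic regression models with and without an interaction of Tech and Touch were reported". H4 (SAP 1.8.1) says the same for OLS.
- **H1 outcome 3 (SAP 1.5.3).** This uses the Full-Tech arms and "therefore only used the Touch predictor in the statistical model". It is outside this point.
- **Full-Tech sub-sample (SAP 1.4.3).** A Touch-only model in Full-Tech is the default. It is switched off for H2, H4 and H3 outcomes 4 and 5, so it remains for H1 outcomes 1-2 and H3 outcomes 1-3. It is not said to test any hypothesis.
- **Hypotheses (Protocol 2.2).** H1 reads "Patients assigned to the High intervention levels for Tech and Touch will demonstrate higher use of MyChart Bedside". No contrast is named.
- **Error control (SAP 1.1).** Every test is at 0.05, without multiplicity adjustment.

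I found no statement of the coding or reference levels, of which model decides, or of whether the interaction test chooses between models. SAP Section 2 adds no rule.

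**The concern.** In a two-by-two factorial trial, a factor's main effect uses all patients. Once a product of 0/1 indicators enters the model, each single-factor coefficient becomes that factor's effect at the reference level of the other. It answers a different question and uses only part of the sample.

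The difference could matter here. High-Touch training goes through every function of the portal (Protocol 3.1.2), and there are 3 selectable functions in Lite and 10 in Full (Protocol 3.1.1). Training may therefore work mainly in Full-Tech. The Equation 1 Touch coefficient would then be near zero while the additive coefficient was not. Where both models are fitted, a reader would have two Tech and two Touch p-values, each with a claim to test the same hypothesis.

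**Working it through.** **The plan's own figure.** Protocol 3.4 plans 3,872 patients to detect changes of 2.2% to 3.8%. Baseline scores, power and sidedness are not given, so this cannot be reproduced. With two halves of 3,872, two-sided 0.05 and 80% power (assumed), the detectable change is 3.79 points at a 75% baseline, 2.54 at 90% and 1.79 at 95%. The range is therefore plausible for a two-group comparison. With 968 v 968 it is 3.50 at 90% and 2.43 at 95%, so the figure does not show which contrast was powered.

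**Inputs.** Tech 60% Full, 40% Lite (Protocol 3.1.3). Touch 1:1 and then 3:1 High to Low (same section), so the share p randomised to High-Touch lies between 0.50 and 0.75. Assumed: 0/1 coding with Lite and Low as reference, independent factors, linear scale, equal variance; hospital clustering and the log or logit link are ignored.

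**Standard errors in residual SD units, N patients.**

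- Touch, additive: 1/sqrt(N p(1-p)). Touch, interacted (Lite only): 1/sqrt(0.4 N p(1-p)). Ratio 1/sqrt(0.4) = 1.58, whatever p is.
- Tech, additive: 1/sqrt(0.24 N). Tech, interacted (Low only): 1/sqrt(0.24 N (1-p)). Ratio 1/sqrt(1-p): 1.41 at p = 0.50 and 2.0 at p = 0.75.

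**Power for an effect common to both levels.** An effect with 80% power in the additive model is 1.96 + 0.84 = 2.80 standard errors. Power in the interacted model is Phi(2.80/ratio - 1.96).

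| Coefficient | SE ratio | Power |
|---|---|---|
| Touch | 1.58 | Phi(-0.19) = 43% |
| Tech, p = 0.50 | 1.41 | Phi(0.02) = 51% |
| Tech, p = 0.75 | 2.0 | Phi(-0.56) = 29% |

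**Table 2 cells, for illustration only.**

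- Touch: sqrt(1/277 + 1/468) = 0.0758, against 1/sqrt(624×1523/2147 + 277×468/745) = 0.0403; ratio 1.88, power 32%.
- Tech: sqrt(1/1523 + 1/468) = 0.0529, against 1/sqrt(624×277/901 + 1523×468/1991) = 0.0426; ratio 1.24, power 62%.

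Table 2 shows 31.2% High-Touch although allocation was 1:1 and then 3:1. The cells therefore appear to follow the reassignment in Protocol 4.3, and are not the ITT groups of SAP 1.4.1.

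**Centered coding (-0.5/+0.5).** Each coefficient becomes the equally weighted mean of two simple effects. At the planned 60:40 by 50:50 allocation the ratios are 1.00 (Tech) and 1.02 (Touch), with power 80% and 78%. At p = 0.75 the Tech ratio is 0.5/sqrt(0.75×0.25) = 1.15, power 68%. On Table 2 cells power is 76% (Tech) and 71% (Touch).

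**Estimand under interaction.** Suppose Touch has a rate ratio of 1.20 in Full and 1.00 in Lite (hypothetical). The Equation 1 coefficient targets 1.00. On Table 2 cells the additive model gives Full a weight of 442.6/(442.6 + 174.0) = 0.718, so it targets exp(0.718 ln 1.2) = 1.14. Averaging over the planned Tech split gives exp(0.6 ln 1.2) = 1.12; equal weights give exp(0.5 ln 1.2) = 1.10.

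**The case against.** **Coding.** The SAP says only that the predictors have two levels. With centered coding the coefficients would be averaged effects and most of the precision loss would go. This stands: the simple-effect reading is an assumption, though the usual one. Until the coding is stated, the coefficients have no defined meaning.

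**The Full-Tech sub-sample.** A reader might infer that the plan would miss a training benefit confined to Full-Tech. For H1 outcomes 1-2 and H3 outcomes 1-3 that does not follow, because SAP 1.4.3 estimates this effect. What remains is that it has no testing role and is not run for H2, H4 or H3 outcomes 4-5.

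**Two models throughout.** It is tempting to say that every outcome yields two competing Tech and two competing Touch results. Two models are explicit only for H2 and H4. H1 outcome 3 has Touch alone. For the other H1 outcomes and H3 the wording may mean one model with the product, as Equations 3 and 4 suggest. In that case no additive main-effect test is specified for them.

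**Transparency.** Reporting both models discloses the choice, which is fair. It does not say which one decides the hypothesis.

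**The hypotheses.** They may mean each factor separately, or the joint High/High arm. The documents do not settle this. If the joint arm is meant, additive main effects are not the test either.

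**Conclusion.** The point holds as a gap in specification that changes both estimand and precision. No passage links a model or coefficient to a hypothesis, and the general model is the one whose single-factor coefficients are, under the usual coding, not main effects. At the planned allocation the cost of reading them as main effects is a standard error about 1.58 times larger for Touch and 1.41-2.0 times larger for Tech, with 80% power falling to about 43% and 51-29%.

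These figures rest on 0/1 coding with Lite and Low as reference, independent factors at the planned split, and a linear equal-variance scale without clustering. The ITT cell counts are not given, so the exact loss is unknown. A reader might take the Table 2 results (1.88 and 1.24; 32% and 62%) as the size of the problem in the main analysis. The documents do not support that, since those cells appear to be counted after Touch reassignment.

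Severity: should-fix.

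**What to change.** In SAP 1.4.2:

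1. State that the Tech and Touch tests of H1 to H4, except H1 outcome 3, come from the model without the product term in the ITT population, and fit that model for every such outcome.
2. State the coding and reference levels.
3. Use the interacted model only for the interaction with its confidence interval and for the four cell estimates. Say that its X_Tech and X_Touch are not read as main effects.
4. If an averaged marginal effect is preferred to the additive coefficient, name it and its weights. The two are not interchangeable under interaction.
5. If the hypotheses mean the joint High/High arm, state that contrast instead.

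The cost is a few sentences. For H2 and H4 both models are already planned; for H1 outcomes 1-2 and H3 the additive model may be an extra fit, with no new data. The downside is that the main effect averages over the other factor if an interaction exists, so the interaction estimate should be shown beside it.
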